2.1. Multiplicity Adjustment

Using a nominal alpha of 2.5% for each of them will ensure the global type I error for the primary objectives is controlled below 2.5%.

3. ANALYSIS SETS

The following analysis sets will be used for this study:

Table 1 **Populations for analyses**

Analysis set	Description
Enrolled set	Participants who were randomized or received study intervention or have undergone an invasive procedure.
Exposed set	All participants who received a study intervention. Analysis per group is based on the study intervention administered.
Per Protocol set	All eligible participants: 
 • who received at least one study intervention as Per Protocol in the control group and all study interventions in the Co-Ad group, • had immunogenicity results pre- and post-dose, • complied with blood draw intervals (mentioned below) (contribution of participants to Per Protocol set at specific timepoint will be defined by timepoint), • without intercurrent medical conditions that may interfere with immunogenicity and, • without prohibited concomitant medication/vaccination.

Intervals for the Co-Ad group: Visit1(D1)-Visit2 (D31) =30-37 days

Intervals for the Control group: Visit1(D1)-Visit2(D31) =30-37 days, Visit2(D31)-Visit3(D45) =12 – 16 days, Visit2(D31)-Visit4(D61) =30-37 days

3.1. Criteria for eliminating data from Analysis Sets

Elimination codes will be used to identify participants to be eliminated from analysis. Detail is provided below for each set.

3.1.1. Elimination from Exposed Set (ES)

Code 1030 (Study intervention not administered at all), 800 (Fraudulent data) and code 900 (invalid informed consent) will be used for identifying participants eliminated from ES (see [Table 2](#)).

3.1.2. Elimination from Per Protocol Set (PPS)

A participant will be excluded from the populations for analysis under the following conditions:

- For codes 800, 900, 1030, 1050 and 2020: participants will be eliminated for all visits.
- For codes 1070, 1080, 1090: participants will be eliminated from a specific visit (at which the condition is met) onwards for the specific group/antigens.
- For codes 1040, 2010, 2040, 2050, 2080: participants will be eliminated from a specific visit (at which the condition is met) onwards.
- For codes 2090, 2100, 2120: participants will be eliminated at the specific visit at which the condition is met. [CCR](#)

Table 2 List of elimination codes

Code	Condition under which the code is used	Visit /Contact(timepoints) where the code is checked	Visit from when it is applicable	Applicable for analysis set/endpoint
800	Fraudulent data	All	All	ES and PPS for analysis of immunogenicity
900	Invalid informed consent	All	All	ES and PPS for analysis of immunogenicity
1030	Study intervention not administered at all	All	All	ES and PPS for analysis of immunogenicity
1040	Administration of concomitant vaccine(s) forbidden in the protocol Use of any investigational or non-registered vaccine other than the study interventions during the period beginning 30 days before the first dose of study interventions, or planned use during the study period. Planned or actual administration of a vaccine not foreseen by the study protocol in the period starting 30 days before the first study intervention administration and ending 30 days after the last study intervention administration.	Visit 1,2 for the Co-ad group. Visit 1,2,3*,4 for the control group	From the specific visit the condition is met	PPS for analysis of immunogenicity

Code	Condition under which the code is used	Visit /Contact(timepoints) where the code is checked	Visit from when it is applicable	Applicable for analysis set/endpoint
	
In the case of COVID-19 vaccines, this time window can be decreased to 14 days before and after each study intervention administration provided this COVID-19 vaccine use is in line with local governmental recommendations.
 
Note: In case an emergency mass vaccination for an unforeseen public health threat (e.g., a pandemic) is recommended and/or organized by the public health authorities, outside the routine immunization program, the time period described above can be reduced if necessary for that vaccine provided it is used according to the local governmental recommendations and that the Sponsor is notified accordingly.
			
1050	
Randomization failure:
 
Participant not randomized in the correct group (To be attributed by Statistician only; Check SBIR, replacement, vaccine administration)
	Visit 1	All	PPS for analysis of immunogenicity
1070	
Vaccine administration not according to protocol
 
Incomplete vaccination course
 
Participant was vaccinated with the correct vaccine but containing a lower volume
 
Wrong replacement or study vaccine administered (not compatible with the vaccine regimen associated to the treatment number)
 
Route of the study vaccine is not intramuscular
 
Side of administration wrong (for Co-ad group if both vaccines are given in the same arm)
 
Wrong reconstitution of administered vaccine
	Vaccination visit(s) 1 or 1 and 2 as applicable	From the specific visit (1 or 2) the condition is met as applicable for the respective group/antigen	PPS for analysis of immunogenicity
1080	
Vaccine temperature deviation
 
Vaccine administered despite a GMP no-go temperature deviation
	Vaccination visit(s) 1 or 1 and 2 as applicable	From the specific visit (1 or 2) the condition is met as applicable for the respective group/antigen	PPS for analysis of immunogenicity
1090	
Expired vaccine administered
	Vaccination visit(s) 1 or 1 and 2 as applicable	From the specific visit (1 or 2) the condition is met as applicable for the respective group/antigen	PPS for analysis of immunogenicity
2010	
Protocol violation linked to inclusion/exclusion criteria
	Visit 1,2 for the Co-ad group.	From the specific visit (1,2,3* or 4)	PPS for analysis of immunogenicity

Code	Condition under which the code is used	Visit /Contact(timepoints) where the code is checked	Visit from when it is applicable	Applicable for analysis set/endpoint
	All inclusion/exclusion criteria defined in the protocol to be checked.	Visit 1,2,3*,4 for the control group	the condition is met.	
2020	All Pre-dose results are missing: RSV-A, RSV-B and HI for the FLU vaccine strains	Co-Ad group: Visit 1 Control group: Visit 1 and Visit 2	All	PPS for analysis of immunogenicity
2040	Administration of any medication forbidden by the protocol Use of any investigational or non-registered product (drug or medical device) other than the study interventions during the period beginning 30 days before the first dose of study interventions, or planned use during the study period. Administration of long-acting immune-modifying drugs or planned administration at any time during the study period (e.g., infliximab). Administration of immunoglobulins and/or any blood products or plasma derivatives planned administration during the study period. Chronic administration (defined as more than 14 consecutive days in total) of immunosuppressants or other immune-modifying drugs planned administration during the study period. For corticosteroids, this will mean prednisone ≥ 20 mg/day, or equivalent. Inhaled and topical steroids are allowed.	Visit 1,2 for the Co-ad group. Visit 1,2,3*,4 for the control group	From the specific visit (1,2,3* or 4) the condition is met	PPS for analysis of immunogenicity
2050	Intercurrent medical condition: Participants may be eliminated from the PPS for immunogenicity if, during the study, they incur a condition that has the capability of altering their immune response (intervent medical condition) or are confirmed to have an alteration of their initial immune status.	Visit 1,2 for the Co-ad group. Visit 1,2,3*,4 for the control group	From the specific visit (1,2,3* or 4) the condition is met	PPS for analysis of immunogenicity
2080	Participants did not comply with vaccination schedule for the control group number of days between dose 1 and dose 2 is outside [30-37 days]	Visit 2	Visit 3 for the control group	PPS for analysis of immunogenicity
2090	Participants did not comply with blood sample schedule: Co-Ad group: Number of days between vaccination (visit1) and blood sample (visit2) is outside [30-37] days Control group: Number of days between vaccination (visit1) and blood sample (visit2) or (visit2) and blood sample (visit4) is outside [30-37] days Or	Visit 2, Visit 3*, Visit 4 as applicable for the group	At the specific visit (2,3* or 4) the condition is met as applicable for the respective group	PPS for analysis of immunogenicity

Code	Condition under which the code is used	Visit /Contact(timepoints) where the code is checked	Visit from when it is applicable	Applicable for analysis set/endpoint
	blood sample (visit2) and blood sample (visit3) are outside [12-16] days			
2100	Serological results not available at the post-dose time point for all antigens tested at that particular time point.	Visit 2,3*,4	At the specific visit (2,3* or 4) the condition is met as applicable for the respective group	PPS for analysis of immunogenicity
2120	Obvious incoherence/abnormality or error in laboratory data Unreliable released data as a result of confirmed sample mismatch or confirmed inappropriate sample handling at lab	Visit 2, Visit 3	At the specific visit (2,3* or 4) the condition is met as applicable for the respective group	PPS for analysis of immunogenicity

ES = exposed set; **GMP** = Good Manufacturing Practices; **HI** = hemagglutination inhibition; **PPS** = Per Protocol set

CCI

4. STATISTICAL ANALYSES

4.1. General Considerations

4.1.1. General Methodology

95% CI for proportion will be based on exact Clopper-Pearson CI [[Clopper](#), 1934].

95% CI for group difference in proportion will be based on Miettinen and Nurminen CI [[Miettinen](#), 1985].

The group adjusted GMT ratio will be based on a back transformation of group contrast in an ANCOVA model applied to the logarithm-transformed titers.

Primary Analysis: The ANCOVA model will include the treatment group and age category (age at vaccination: 65-69, 70-79 or ≥ 80 years) as fixed effects and the pre-dose log-10 titer as regressors.

Sensitivity Analysis: The ANCOVA model will include the treatment group and age category (age at vaccination: 65-69, 70-79 or ≥ 80 years) as fixed effects, center as the random effect and the pre-dose log-10 titer as regressors.

95% CI for GMT and GMT ratio will be based on a back transformation of student CI for the mean and difference of means (for GMT ratio) respectively of log-transformation (i.e., $10^{\wedge}CI$).

4.1.2. Definition:

- For all endpoints:

The baseline value will be the latest pre-dose assessment with a non-missing value, including those from unscheduled visits. If time is not collected, Day 1 assessments are assumed to be taken prior to first dose and used as baseline.

MG1 (mean geometric increase): The geometric mean of the within participant ratios of the post-dose titer over the pre-dose titer.

- For the RSV antigens:

A seronegative participant will be defined as a participant whose antibody titer/concentration is below the cut-off value of the assay. A seropositive participant is a participant whose antibody titer/concentration is greater than or equal to the cut-off value of the assay.

- For the FLU antigens:

SCR (seroconversion rate): The percentage of vaccinees who have either a HI pre-dose titer $< 1:10$ and a post-dose titer $\geq 1:40$ or a pre-dose titer $\geq 1:10$ and at least a four-fold increase in post-dose titer.

HI SPR (seroprotection rate): The percentage of vaccinees with a serum HI titer $\geq 1:40$ that usually is accepted as indicating protection.

4.2. Primary Endpoints Analyses

The primary analysis will be based on the PPS for analysis of immunogenicity. If, in any vaccine group, the percentage of vaccinated participants with serological results excluded from the PPS for analysis of immunogenicity is 5% or more, a second analysis based on the ES will be performed to complement the PPS analysis.

4.2.1. Between groups assessment

- The 2-sided 95% CI for the group GMT ratio in terms of HI antibody titers for each of the FLU vaccine strains between RSVPreF3 OA investigational vaccine administered alone (Control group) over RSVPreF3 OA investigational vaccine when co-administered with the FLU vaccine (Co-Ad group) will be computed at 1 month after the FLU vaccine (i.e., at Day 31 [Visit 2] for both groups).
- The 2-sided 95% CI for the group GMT ratio in terms of RSV-A neutralizing antibody titers between RSVPreF3 OA investigational vaccine administered alone (Control group) over RSVPreF3 OA investigational vaccine when co-administered with the FLU vaccine (Co-Ad group) will be computed at 1 month after the RSVPreF3 OA investigational vaccine dose (i.e., at Day 31 [Visit 2] for the Co-Ad group and at Day 61 [Visit 4] for the Control group).
- The 2-sided 95% CI for the group GMT ratio in terms of RSV-B neutralizing antibody titers between RSVPreF3 OA investigational vaccine administered alone (Control group) over RSVPreF3 OA investigational vaccine when co-administered with the FLU vaccine (Co-Ad group) will be computed at 1 month after the

RSVPreF3 OA investigational vaccine dose (i.e., at Day 31 [Visit 2] for the Co-Ad group and at Day 61 [Visit 4] for the Control group).

The results will be presented in tables as well as graphs using forest plots.

4.2.2. Main analytical approach

The 2-sided 95% CI for group adjusted GMT ratio will be derived from **an ANCOVA model on \log_{10} transformed titer**. The model will include the treatment group and age category (age at vaccination: 65-69, 70-79 or ≥ 80 years) as fixed effects, and the pre-dose \log_{10} -transformed titer as covariate. Missing data will not be replaced. Titers below the assay cut-off will be replaced by half the assay cut-off, titers above the upper limit of quantification (ULOQ) will be replaced by the ULOQ.

Success criteria for non-inferiority and testing sequence:

The following testing sequence will be used:

1st sequence:

- The upper limit of the 2-sided 95% CI of the GMT ratio (Control group divided by Co-Ad group) for each of the FLU vaccine strains are ≤ 1.5 .

AND

- The upper limit of the 2-sided 95% CI of the GMT ratio (Control group divided by Co-Ad group) for RSV-A neutralization antibodies is ≤ 1.5 .

2nd sequence:

- The upper limit of the 2-sided 95% CI of the GMT ratio (Control group divided by Co-Ad group) for RSV-B neutralization antibodies is ≤ 1.5 .

Testing will progress in the 2nd sequence only if the 1st sequence is a success, so that no further adjustment of alpha is required.

Here is an example of SAS code that will be used:

```
proc mixed data=data_in;
  class agecat trt_grp;
  model log10(titer day x) = log10(pre_dose) agecat trt_grp;
  lsmeans trt_grp/cl pdiff alpha=0.05;
  run;
```

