6.3.3. Intervention allocation to the participant

An automated Internet-based system, SBIR will be used for randomization and for identification of intervention material. The randomization algorithm will use a minimization procedure accounting for age (65-69, 70-79 or ≥ 80 years) and center. Minimization factors will have equal weight in the minimization algorithm. Refer to Section 4.1.2 for the enrollment rules.

Once a participant identification number is allocated, the randomization system will determine study group and will provide the study intervention number to be used for the

first dose. The study intervention numbers to be used for subsequent dosing will be provided by the same automated Internet-based system (SBIR).

When SBIR is not available, please refer to the SBIR user guide or SPM for specific instructions.

Refer to the SPM for additional information about the study intervention number allocation.

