9.3.1. Primary endpoints/estimands analysis (Amended: 13 December 2022)

The primary endpoints/estimands are described in Section [3](#). The confirmatory analyses of non-inferiority will be based on the PPS.

- Method for non-inferiority of the FLU vaccine in terms of HI GMT ratio for each of the FLU vaccine strains at one month after the FLU vaccine dose (i.e., at Day 31 for both groups):

The 2-sided 95% confidence interval (CI) for Group GMT ratio between the FLU vaccine administered alone (Control group) over the RSVPreF3 OA investigational vaccine when co-administered with the FLU vaccine (Co-Ad group) will be derived from an ANCOVA model* on \log_{10} transformed titer.

- Method for non-inferiority of RSV investigational vaccine in terms of RSV-A neutralization antibody GMT ratio at one month after the RSVPreF3 OA investigational vaccine dose (i.e., at Day 31 for the Co-Ad group and at Day 61 for the Control group):

The 2-sided 95% CI for Group GMT ratio between the RSVPreF3 OA investigational vaccine administered alone (Control group) over the RSVPreF3 OA investigational vaccine when co-administered with the FLU vaccine (Co-Ad group) will be derived from an ANCOVA model* on \log_{10} transformed titer.

- Method for non-inferiority of RSV investigational vaccine in terms of RSV-B neutralization antibody GMT ratio at 1 month after the RSVPreF3 OA investigational vaccine dose (i.e., at Day 31 for the Co-Ad group and at Day 61 for the Control group).*

The 2-sided 95% CI for Group GMT ratio between the RSVPreF3 OA investigational vaccine administered alone (Control group) over the RSVPreF3 OA investigational vaccine when co-administered with the FLU vaccine (Co-Ad group) will be derived from an ANCOVA model on \log_{10} transformed titer.*

**The model will include the treatment group and age category (age at vaccination: 65-69, 70-79 or ≥ 80 years) as fixed effects, and the pre-dose \log_{10} -transformed titer as covariate. Missing data will not be replaced. Titors below the assay cut-off will be replaced by half the assay cut-off; titers above the upper limit of quantification (ULOQ) will be replaced by the ULOQ.*

Success criteria for non-inferiority **and testing sequence**:

The following testing sequence will be used:

- Sequence 1:***
 - The upper limit (UL) of the 2-sided 95% CI on the Group GMT ratio (Control group divided by Co-Ad group) for each of the FLU vaccine strains are ≤ 1.5 .

AND

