4.2.3. Sensitivity analyses

As for the main analytical approach an ANCOVA model will be performed with the treatment group and age category (age at vaccination: 65-69, 70-79 or ≥ 80 years) as fixed effects, **center as random effect** and the pre-dose \log_{10} -transformed titer as covariate.

In case the model with random effect does not converge we proceed with center as a fixed effect.

Here is an example of SAS code that will be used:

```
proc mixed data=data_in;
  class agecat trt_grp center;
  model log10(titer day x) = log10(pre_dose) agecat trt_grp;
  random intercept/subject=center;
  lsmeans trt_grp/cl pdiff alpha=0.05;
run;
```

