5. SAMPLE SIZE DETERMINATION

The **target enrollment** will be **1028 participants** (514 in the group receiving the RSVPreF3 OA investigational vaccine co-administered with FLU aQIV [Co-Ad group] and 514 in the Control group where RSVPreF3 OA investigational vaccine and FLU aQIV are administered in a sequential manner). This allows to obtain at least 924 **evaluable participants** (462 in the Co-Ad group and 462 in the Control group) for the

evaluation of the primary objectives, assuming that 10% of the enrolled participants will not be evaluable.

Participants who withdraw from the study will not be replaced.

Each objective will be evaluated with a nominal type I error of 2.5%.

Table 3 Overall power to demonstrate primary objectives: non-inferiority of the immunogenicity of the RSVPreF3 OA investigational vaccine when co-administered with FLU aQIV compared to when administered alone – assuming approximately 462 participants are available in each group

Endpoint	Standard deviation of \log_{10} concentration	Reference ratio	Non inferiority margin	Type II error	Power
FLU non-inferiority* (1-sided test with alpha=2.5%)					
GMTs HI H1N1 strain	0.6	1.05	1.5	2.5%	97.5%
GMTs HI H3N2 strain	0.6	1.05	1.5	2.5%	97.5%
GMTs HI B/Yamagata	0.6	1.05	1.5	2.5%	97.5%
GMTs HI B/Victoria strain	0.6	1.05	1.5	2.5%	97.5%
RSV non-inferiority* (1-sided test with alpha = 2.5%)					
GMTs RSV-A neutralization antibody	0.45	1.05	1.5	0.1%	99.9%
RSV non-inferiority* (1-sided test with alpha = 2.5%)					
GMTs RSV-B neutralization antibody	0.45	1.05	1.5	0.1%	99.9%
Global Type II error to show non-inferiority				~10.0%	
Global power					~90.0%

GMT = geometric mean titer; **HI** = hemagglutination inhibition; **RSV** = respiratory syncytial virus

*Pass 2019 alpha = 2.5%, Two-Sample T-Tests for Non-Inferiority Assuming Equal Variance and Equal mean

For RSV: non-inferiority limit = 0.176 (=log10[1.5]).

For each FLU vaccine strain: non-inferiority limit = 0.176 (=log10[1.5]).

Reference Ratio= 0.0212 (=log10[1.05])

Considering a potential slight interference of 1.05 in true GMTs in both groups with a common population standard error of 0.45 for the RSV-A and RSV-B neutralization antibodies and 0.6 for each of the FLU strains in \log_{10} transformed concentration, the study has at least 90.0% power to meet the primary objectives.

Nominal powers to evaluate the secondary objective

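### Center is one of two equally weighted minimization factors but is left out of the primary ANCOVA; if titers differ by center, the six primary confidence intervals are slightly too wide.

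*SAP*

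**What the plan says.** Protocol 6.3.3 allocates participants by a "minimization procedure accounting for age (65-69, 70-79 or ≥ 80 years) and center", and adds: "Minimization factors will have equal weight in the minimization algorithm".

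The primary model is the same in Protocol 9.3.1, SAP 4.1.1 and SAP 4.2.2. In the words of SAP 4.2.2, "The model will include the treatment group and age category (age at vaccination: 65-69, 70-79 or ≥ 80 years) as fixed effects", with pre-dose log10 titer as covariate. The SAS code there has age category and treatment group as its only class variables. The success criteria and the testing sequence are set out in the same section and so attach to this model.

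SAP 4.1.1 and 4.2.3 also specify and code the same model with "center as the random effect and the pre-dose log-10 titer as regressors", but only as a sensitivity analysis. Its fallback reads: "In case the model with random effect does not converge we proceed with center as a fixed effect". Neither document says why one minimization factor is in the primary model and the other is not.

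**The concern.** An analysis should normally reflect the restrictions placed on the randomization. When the groups are balanced within center, a difference in titer level between centers affects both groups about equally and largely cancels from the group contrast. A model without center does not know this. It leaves the between-center variance in the residual and reports a standard error larger than the true one.

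Success requires the upper limits for four influenza strains and RSV-A to be at or below 1.5 together, and then the same for RSV-B. Needless width therefore counts on every endpoint, and the sensitivity model cannot rescue a near miss. The error is in the safe direction for non-inferiority: a false claim becomes less likely, not more. What is at stake is calibration and a little power.

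**Working it through.** **Inputs from the documents** (SAP 5, Protocol 9.5): 462 evaluable per group; margin 1.5 (log10 = 0.1761); true ratio 1.05 (log10 = 0.0212); SD of log10 titer 0.6 for each influenza strain and 0.45 for RSV-A and RSV-B; one-sided alpha 2.5%. The distance to the margin is d = 0.1761 − 0.0212 = 0.1549.

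**Assumed, because the documents give no value:** the share of variance lying between centers after age and pre-dose titer (ICC), taken as 0, 0.02, 0.05 or 0.10.

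**Step 1: reproduce the plan.** SE = SD × √(2/462), which is 0.03948 for influenza and 0.02961 for RSV. Power = Φ(d/SE − 1.96):
- influenza: Φ(3.924 − 1.96) = 97.5% per strain;
- RSV: Φ(5.232 − 1.96) = 99.9% each.

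Summing type II errors gives a global power of 1 − (4 × 0.0248 + 2 × 0.0005) = 90.0%. The product of the six powers is 90.4%. The plan's 97.5%, 99.9% and ~90.0% are all reproduced.

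**Step 2: effect of omitting center.** Let SEm be the SE that the model without center reports, and SEt = SEm × √(1 − ICC) the true SE under within-center balance.
- Excess width = 1/√(1 − ICC) − 1
- One-sided type I error = 1 − Φ(1.96/√(1 − ICC))
- Power without center = Φ((d − 1.96 × SEm)/SEt)
- Power with center = Φ(d/SEt − 1.96)

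Example, one influenza strain at ICC 0.05: SEt = 0.03948 × √0.95 = 0.03848. Without center, (0.1549 − 0.0774)/0.03848 = 2.015, which gives 97.8%. With center, 0.1549/0.03848 − 1.96 = 2.066, which gives 98.1%.

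| ICC | CI too wide by | Type I error | Per-strain power, without / with | Global power (product), without / with | Gain (points) |
|---|---|---|---|---|---|
| 0 | 0% | 2.50% | 97.5 / 97.5% | 90.4 / 90.4% | 0 |
| 0.02 | 1.0% | 2.39% | 97.6 / 97.7% | 90.8 / 91.2% | 0.4 |
| 0.05 | 2.6% | 2.22% | 97.8 / 98.1% | 91.4 / 92.4% | 1.0 |
| 0.10 | 5.4% | 1.94% | 98.1 / 98.5% | 92.5 / 94.2% | 1.7 |

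Power for RSV-A and RSV-B is at least 99.9% throughout.

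**Step 3: allow for the pre-dose covariate.** Step 2 treats the stated SDs as residual SDs. If they are marginal SDs and the pre/post correlation is r (assumed), the residual SD is SD × √(1 − r²). At r = 0.5, global power over the same ICC range is 98.0 to 98.7% without center and 98.0 to 99.0% with it, a gain of 0 to 0.4 point. At r = 0.7 the gain is about 0.01 point.

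**Step 4: check by simulation.** Trials were simulated with minimization on age and center at equal weight (biased coin 0.9 and 40 centers, both assumed), 1028 randomized, 10% lost, SD 0.6 and the true ratio set at the margin. Pre-dose titer and age were in both models, and center was fitted as a fixed effect. There were 3000 runs per setting; the Monte Carlo SE is about 0.3 point for the one-sided error.

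| ICC | Type I error, without / with center | Mean CI width (log10), without / with center |
|---|---|---|
| 0 | 2.50 / 2.47% | 0.1548 / 0.1554 |
| 0.05 | 2.47 / 2.63% | 0.1549 / 0.1516 |
| 0.10 | 2.00 / 2.40% | 0.1547 / 0.1476 |

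Under simple randomization at ICC 0.10, the model without center had a type I error of 2.53%. The conservatism therefore comes from balancing on center and then ignoring it. No bias in the estimated ratio was seen.

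**The case against.** The strongest reply is that this is an efficiency preference, not a defect. The center-adjusted model is already pre-specified, so any dependence on center will be seen. Wider intervals are the safe side in a non-inferiority trial. The planned power comes from a calculation without center ("Two-Sample T-Tests for Non-Inferiority Assuming Equal Variance and Equal mean") and is met. The ICC is unknown and may be zero. The stated SDs read most naturally as marginal, so the smaller gains in step 3 describe the planned ANCOVA better than those in step 2. At ICC 0.05 the simulated type I error cannot be told apart from 2.5%. Finally, a mixed model with a convergence fallback could leave some of the six endpoints with random center and others with fixed center, whereas the current primary is one fixed model.

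Most of this stands, and it limits the point to an optional improvement. It does not remove the point. The sensitivity model does not decide success: if a primary upper limit just misses 1.5 and the center-adjusted limit meets it, the trial has still failed. The width effect follows directly from the balance that the allocation is designed to produce. The fallback is already pre-specified, so the choice between random and fixed center follows a stated rule.

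**Conclusion.** The point holds, and its consequence is small. Center is a full minimization factor, the primary model omits it without a stated reason, and the resulting error is conservative. For a residual center ICC up to 0.10, the six intervals are up to 5.4% too wide and one-sided type I error falls to no less than 1.9%. The global power forgone is at most 1.7 points if the stated SDs are residual, and at most 0.4 point if they are marginal with a pre/post correlation of 0.5. If no center variance remains after age and pre-dose titer, there is no effect.

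These sizes rest on assumed ICC and correlation values, a normal approximation and near-complete balance within center. The direction rests only on that balance and on some center variance remaining.

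**What to change.** Make the SAP 4.2.3 model the primary analysis for all six GMT ratios: treatment group, age category, pre-dose log10 titer and center as a random effect, with the stated fixed-effect fallback. Keep the model without center as the sensitivity analysis. SAP 4.1.1, 4.2.2 and 4.2.3 and the model footnote in Protocol 9.3.1 need matching edits, made before the data are analyzed.

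Both models are already written and coded, so this is a change of wording with no new data or participants. Two costs remain: the protocol edit is an amendment that needs ethics approval under Protocol 10.1.1, and the primary analysis takes on a convergence contingency that it does not have now. If the sponsor prefers to keep the present model for its simplicity, one sentence in SAP 4.2.2 giving the reason for omitting center, and noting that the omission is conservative, would at least put the choice on record.
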